### **3.4 Analysis Visit Windowing Rules**

The actual visit for a subject may not exactly coincide with their targeted visit date. The actual visit date will be mapped to the study visit following the analysis visit windowing rules below. Unless specified otherwise, all efficacy and safety analyses will be based on the analysis visits. If there are multiple records fall within the same defined analysis visit window, the non-missing record closest to the target day will be considered for the analysis.

If two non-missing assessment actual dates are equidistant from the target day, the later visit will be considered for analysis.

Composite endpoints (e.g. CDAI score) will be calculated for each date at which individual components are being measured before applying the analysis visit windows rather than to calculate visit window based individual component.

### 3.4.1 DB Treatment Period

DB Period Study Day 1 is defined as the first day of DB IP administration. For subjects who are randomized but not dosed after randomization, the Day 1 is defined as the date of randomization.

DB Period Study Day is defined as the number of days from the Double-Blind Period Study Day 1.

- Before DB Period Study Day 1:  
Double-Blind Period Study Day = (Date of Interest – Date of DB Period Study Day 1)

- On or After DB Period Study Day 1:  
DB Period Study Day = (Date of Interest – Date of DB Period Study Day 1) + 1

Unless otherwise specified, all efficacy analysis will apply the analysis visit window rules as defined in [REDACTED]

[REDACTED]

[REDACTED]	[REDACTED]	[REDACTED]	[REDACTED]	[REDACTED]
[REDACTED]	[REDACTED]	[REDACTED]	[REDACTED]	[REDACTED]
	[REDACTED]	[REDACTED]	[REDACTED]	[REDACTED]
	[REDACTED]	[REDACTED]	[REDACTED]	[REDACTED]
	[REDACTED]	[REDACTED]	[REDACTED]	[REDACTED]
	[REDACTED]	[REDACTED]	[REDACTED]	[REDACTED]
	[REDACTED]	[REDACTED]	[REDACTED]	[REDACTED]
	[REDACTED]	[REDACTED]	[REDACTED]	[REDACTED]
	[REDACTED]	[REDACTED]	[REDACTED]	[REDACTED]
	[REDACTED]	[REDACTED]	[REDACTED]	[REDACTED]
	[REDACTED]	[REDACTED]	[REDACTED]	[REDACTED]

[REDACTED]

[REDACTED]

[figure not shown]
[figure not shown]
[REDACTED]

[REDACTED]

[REDACTED]

[REDACTED]	[REDACTED]	[REDACTED]	[REDACTED]	[REDACTED]
[REDACTED]	[REDACTED]	[REDACTED]	[REDACTED]	[REDACTED]

[figure not shown]

### **3.4.2 OL Treatment Period**

OL Period Study Day 1 is defined as the first day of OL IP administration. OL Period Study Day is defined as the number of days from OL Period Study Day 1.

- Before OL Period Study Day 1:  
Open-Label Period Study Day = (Date of Interest – Date of OL Period Study Day 1)
- On or After OL Period Study Day 1:  
OL Period Study Day = (Date of Interest – Date of OL Period Study Day 1) + 1.

## **3.5 Study Subjects**

### **3.5.1 Subject Disposition and Completion Status**

A summary of subject disposition throughout the study with respect to completion of double-blind induction and maintenance periods and open-label period will be provided. The number and percentage will be provided by treatment groups and overall using the ITT population and OL population, respectively. The timing of and reasons for early withdrawal from treatment and from study will be tabulated and listed.

### **3.5.2 Demographics and Baseline Characteristics**

Subject demographics and baseline characteristics will be listed for each subject. Following demographics and baseline characteristics will be summarized by treatment groups and overall using the ITT population and OL population, respectively. A summary of baseline disease characteristics may include, but not be limited to:

- Age
- Age (< 40 years, ≥ 40 years)
- Sex (Male, Female)
- Race (White, Black/African American, Asian, Other)
- Race (White, Non-white)
- Region (US, Non-US)
- Disease duration of CD (years)
- Disease duration (< 2 years, ≥ 2 years )
- Disease duration (< 5 years, ≥ 5 years )
- Ethnic group (Hispanic or Latino, Other)
- Height (cm)
- Weight (kg)
- BMI (kg/m^2)

- Baseline disease location (ileum, not colon; colon, not ileum; or ileo-colonic, as observed at baseline ileocolonoscopy)
- Baseline CDAI score
- Baseline weekly abdominal pain score
- Baseline weekly loose/liquid stool count
- Baseline SES-CD score
- Baseline SES-CD score by baseline disease location subgroup (per subgroup of subjects with ileum, not colon; colon, not ileum; or ileo-colonic disease)
- Baseline CRP (mg/L)
- Baseline CRP ( $< 5$  mg/L,  $\geq 5$  mg/L)
- Baseline fecal calprotectin ( $\mu\text{g/g}$ )
- Baseline fecal calprotectin ( $< 250$   $\mu\text{g/g}$ ,  $\geq 250$   $\mu\text{g/g}$ )
- Baseline fecal calprotectin ( $< 200$   $\mu\text{g/g}$ ,  $\geq 200$   $\mu\text{g/g}$ )
- Baseline IL22 (unit)
- XXXXXXXXXX
- Baseline IBDQ score
- Alcohol status(Never, Current and Former)
- Number of prior use of anti-TNF agents (1,  $> 1$ )
- Number of prior use of anti-TNF $\alpha$  agents (1, 2,  $\geq 3$ )
- Prior use of vedolizumab (Yes, No)
- Use of 5-aminosalicylates at baseline (Yes, No)
- Use of corticosteroids at baseline (Yes, No)
- Use of immunomodulators at baseline (Yes, No)
- Smoking status at baseline (Never, Current, Former)

### 3.5.3 Study Drug Exposure

Descriptive statistics for extent of exposure (in days) will be presented for the as-treated population and the OL population during the specified treatment period.

For DB period, the following summaries will be provided using for the as-treated population:

- Duration of exposure in the DB period

- Number of doses received
- Number and percentage of subjects received the entire dose

For OL period, the following summaries will be provided using the OL population:

- Duration of exposure in the OL period
- Number of doses received
- Number and percentage of subjects received the entire dose by visit

Additionally, descriptive statistics for the cumulative exposure for overall MEDI2070 will be provided. If a subject entered both the DB period and OL period, the subject will be considered as the same subject and the exposure data will be combined from both periods.

### **3.5.4 Prior and Concomitant Medications**

*Prior medication* refers to all medications that were started prior to the start of the first dose of investigational product.

*Concomitant medication* refers to all medications taken during the treatment period of the DB period and the OL period. Concomitant medications include medications continued from pre-treatment. Medications with missing start and stop dates will be counted as concomitant medications. Medications with partial start or stop dates will be handled as described in Section 3.3.1. Medications with start and stop dates which bracket the first dose date will be summarized as both prior and concomitant medications.

All prior and concomitant medications data will be coded by Medimmune approved drug dictionary (AstraZeneca Drug Dictionary or WHODrug) and listed for each subject by treatment groups. The number and percentage of subjects taking at least one prior or concomitant medication will be presented by Preferred Term (PT) and treatment group for the DB and OL treatment periods using the ITT population and the OL population, respectively. The following summary tables will be provided for the prior and concomitant medications:

- Prior disease related treatments
- Concomitant medication taken for CD
- Concomitant medications for reason other than CD
- Disallowed concomitant medications

In addition, the number and percentage of subjects receiving the following selected medications: 5- aminosalicylates, prednisone, and immunomodulators (e.g. methotrexate, azathioprine, and 6-mercaptopurine) will be summarized for each treatment group as coded. The dose level of oral corticosteroid will be summarized by visit.

### **3.5.5 CD History**

The CD history will be summarized descriptively using the ITT population. In particular,

- Summary of Crohn's location by category for current, at the original diagnosis, and at any past time. The Crohn's location categories include Colon, not ileum; Ileocolonic (ileum and colon); Ileum, not colon; Extra-intestinal.
- Summary of subjects with anti-TNF use
  - Number and percentage of subjects with anti-TNF use
  - Number and percentage of subjects with prior use of following anti-TNF: Infliximab, Adalimumab, Certolizumab pegol, Golimumab.
  - Descriptive summary of time since first use of anti-TNF by type of anti-TNF
  - Number and percentage of subjects by primary reason for stopping prior anti-TNF: Primary failure, Secondary failure, Intolerance, Not applicable, Other
- Summary of subjects with biologics agents other than anti-TNF agents
  - Number and percentage of subjects with biologics agents other than anti-TNF agents
  - Number and percentage of subjects with prior use of Vedolizumab
  - Number and percentage of subjects by primary reason for stopping prior Vedolizumab: Primary failure, Secondary failure, Intolerance, Not applicable, Other
- Summary of subjects with immunomodulator
  - Number and percentage of subjects with prior immunomodulator
  - Number and percentage of subjects with prior use of following immunomodulator: Methotrexate, Azathioprine, 6-mercaptopurine, Other
  - Descriptive summary of time since first use of immunomodulator
- Summary of subjects with fistula and stricture/obstruction
  - Number and percentage of subjects with history of fistula
  - Number and percentage of subjects with fistula at baseline
  - Number and percentage of subjects with stricture/obstruction

### **3.5.6 Medical and Surgical History**

The MedDRA Preferred Term (PT) in the medical history and surgical history will be summarized by the number and percentage of subjects for each treatment group and overall using the ITT population.

### **3.5.7 Physical, Neurological and Visual Examination**

All data related to physical, neurological and visual examination will be listed for each subject.

The physical and neurological examination will be summarized by visit and treatment groups using the ITT population and the OL population respectively. Frequency count and percentages will be presented.

The visual examination will include following parameters:

- Best corrected near vision (Right eye, Left eye)
- Best corrected distance vision (Right eye, Left eye)

Summary statistics of best corrected near and distance vision for both eyes will be presented using the decimal format of the acuity notation. The visual acuity notation conversions can be found in Appendix. Change from baseline will be calculated and categorized as  $< 0$  (worsened vision),  $0$  (no change) and  $> 0$  (improved vision). Frequency count and percentages based on the defined categories will be presented.

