### **1.5.1 Benefit-risk Assessment**

Results from previous clinical studies have provided safety and tolerability data for MEDI2070 and shown significantly greater efficacy for MEDI2070 compared with placebo for achieving CDAI response, CDAI 100-point improvement, and decreases in C-reactive protein (CRP) and fecal calprotectin (Study CD-IA-MEDI2070-1147). No safety risk of MEDI2070 was identified. In Study CD-IA-MEDI2070-1147, TEAEs, TEAEs of  $\geq$  Grade 3 severity, TESAEs and TEAEs leading to discontinuation of investigational product occurred in equivalent numbers of subjects in the placebo and MEDI2070 groups. TEAEs related to investigational product and adverse events of special interest (AESIs), including infections, were more common in the placebo group. The combination of observed efficacy and apparent safety in the Phase 2a study (CD-IA-MEDI2070-1147) suggests an acceptable benefit-risk balance to justify exposing approximately 5-fold more subjects with moderate to severe CD to the range of doses planned in this study.

Although no safety risks for MEDI2070 have been identified, the immunoregulatory role of IL-23 in humans is not completely understood. Potential risks include infections, malignancies, complications associated with vaccination, infusion reactions, injection-site reactions, hypersensitivity, immune complex disease, and neurological and visual toxicities. Subjects will be closely monitored during the study with regular full blood analysis including differential white cell count and serum chemistry to monitor the risk of infection. Visual acuity tests, ophthalmoscopy, and complete physical and neurologic examinations will be performed at screening and during the study. In addition, live/attenuated vaccinations will not be permitted during the study. Exclusion criteria have been formulated to ensure that subjects at increased potential risk due to the mechanism of action of MEDI2070 are not enrolled in the study.

In addition, an independent Data Monitoring Committee (DMC) will monitor and protect the safety of the subjects through review of safety data on a regular basis throughout the double-blind period of the study; ie, until the last subject completes Week 28 (see Section 4.8.9).

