## 2.2.4 Safety Endpoints

1. Incidence and severity of TEAEs
2. Incidence of TESAEs
3. Incidence and severity of treatment-emergent AESIs, including:
  - a. Incidence and severity of infusion/injection-site reactions
  - b. Incidence and severity of hypersensitivity reactions
  - c. Incidence of malignancies
  - d. Major cardiac events, defined as myocardial infarction, stroke, or cardiovascular death
  - e. Incidence and severity of ocular AEs, including cataracts
4. Incidence of AEs leading to investigational product discontinuation
5. Incidence of specific laboratory abnormalities

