#### **4.3.3.4 Visual Acuity Tests and Ophthalmoscopy Examination**

The visual acuity test and ophthalmoscopic examination should be performed according to the Schedule of Study Procedures in [REDACTED]. The visual acuity test will be used to determine the smallest letters a person can read on a standardized chart (eg, Snellen chart or other suitable chart) or a card held 4 to 6 meters (14 to 20 feet) away. The test should be done in a health care provider's office or other suitable environment. The subject will be asked to stand or sit approximately 6 meters (20 feet) from the eye chart with both eyes open. One eye should be gently covered while the subject reads out loud the smallest line of letters they can see on the chart. Best corrected visual acuity (use of corrective refractive lenses is permitted) should be recorded.

The ophthalmoscopic examination should include visually magnified inspection of the internal eye structures and also assessment of the quality of the eye's red reflex after the pupil has been dilated. The appearance of the optic disc and retinal vasculature should be examined and any anomalies in the appearance of the internal ocular structures should be recorded. The presence or absence of cataracts should be noted.

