### **3.5.7 Physical, Neurological and Visual Examination**

All data related to physical, neurological and visual examination will be listed for each subject.

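### The original SAP's visual acuity table counts any fall in decimal acuity as worsening, with no size band, so trivial and severe losses share one cell (minor)

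*Combined protocol and SAP*

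**What the plan says.** **Why acuity is measured.** Protocol 1.5.1 includes in its list of potential risks "immune complex disease, and neurological and visual toxicities", and names acuity tests and ophthalmoscopy among the monitoring measures. Protocol 2.2.4 has as a safety endpoint "Incidence and severity of ocular AEs, including cataracts".

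**How it is measured.** Protocol 4.3.3.4 allows a "standardized chart (eg, Snellen chart or other suitable chart"). Under original SAP Appendix 6.4, notation may differ between sites, and each site converts its own reading to a decimal before entry. The readable text gives no rounding rule.

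**How it is analysed in the original SAP.** Section 3.5.7 covers near and distance vision in each eye and plans three outputs:

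- A listing: "All data related to physical, neurological and visual examination will be listed for each subject".
- Summary statistics: "Summary statistics of best corrected near and distance vision for both eyes will be presented using the decimal format of the acuity notation".
- A change table: "Change from baseline will be calculated and categorized as" worsened (below zero), no change (zero) or improved (above zero). Then: "Frequency count and percentages based on the defined categories will be presented".

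No minimum change, severity band or analysis population is stated for the visual summaries.

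**How it is analysed in the later SAP.** This version was written after early termination with 29 subjects randomized. Its section 3.5.7 keeps only the listing.

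**The concern.** A cut-point at zero records direction and discards size. For a risk named in advance, the useful question is how many eyes lost a meaningful amount of vision in each arm, and a three-way sign count cannot say. Small retest differences and rounding fall in the same cell as a severe loss. A few severe cases would then be a small excess on top of a background count present in every arm.

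The decimal scale adds a second difficulty. It is a ratio scale, so equal decimal differences are not equal losses of vision. A better cut-point on the decimal difference would therefore still misrank losses between eyes with good and poor baseline vision.

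**Working it through.** The plan states no retest variability, no meaningful loss and no expected rate of worsening, so it has no figure to reproduce. Throughout, logMAR = −log10(decimal acuity), and one line is taken as 0.1 logMAR.

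**Step 1. Apply the rule to example changes.** Loss = log10(baseline / follow-up).

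| Baseline to follow-up | Decimal change | Loss (logMAR) | Lines | SAP class |
|---|---|---|---|---|
| 1.0 to 0.99 | −0.01 | 0.004 | 0.04 | worsened |
| 1.0 to 0.8 | −0.20 | 0.097 | about 1 | worsened |
| 0.2 to 0.1 | −0.10 | 0.301 | about 3 | worsened |
| 1.0 to 0.1 | −0.90 | 1.000 | 10 | worsened |

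All four fall in one cell. Rows two and three show the scale problem: the three-line loss has the smaller decimal change.

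**Step 2. Rounding alone.** A reading of 20/30 is 0.667. If it is entered as 0.7 at one visit and 0.67 at the next, the change is −0.03 and the eye is classed as worsened, although the reading is identical. This needs no assumption about retest error.

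**Step 3. Retest variation (illustration).** Assume no true change, a normal retest difference with mean 0 and SD s, and a difference rounded to the nearest 0.1 logMAR. An eye is classed as worsened when the unrounded loss exceeds 0.05, so the probability is Φ(−0.05/s). It shows a loss of at least 0.3 logMAR when the unrounded loss exceeds 0.25, so the probability is Φ(−0.25/s).

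| s (assumed) | Any loss | Loss ≥ 0.3 logMAR |
|---|---|---|
| 0.05 | Φ(−1.00) = 15.9% | Φ(−5.00) < 0.1% |
| 0.08 | Φ(−0.625) = 26.6% | Φ(−3.125) = 0.1% |
| 0.10 | Φ(−0.50) = 30.9% | Φ(−2.50) = 0.6% |

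A separate simulation rounded each of the two readings rather than their difference, with s from 0.03 to 0.10. It gave 12% to 32% for any loss and 0% to 0.8% for three lines or more. In an arm of 76, counting one eye per subject, 12% to 32% is about 9 to 24 eyes.

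**Step 4. What the noise does to the cell (illustration).** Suppose 5% of a 76-subject active arm has true severe loss, placebo has none, and 20% of the remaining eyes are classed as worsened by noise.

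- Placebo: 0.20 × 76 = 15.2.
- Active: (0.05 + 0.95 × 0.20) × 76 = 0.24 × 76 = 18.2.
- Without noise the comparison would be 3.8 against 0.
- Severe cases make up 0.05/0.24 = 21% of the active cell.

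**The case against.** The strongest reply is that the table is one output among several.

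- The same section lists every visual value and summarizes acuity on the decimal scale. The formatting conventions in original SAP 3.1 include minimum and maximum.
- Ocular adverse events are a safety endpoint with severity. They are also an event category of special interest (Protocol 5.3.3; original SAP 3.9.2), reportable within 24 hours even if nonserious (Protocol 5.6.3).
- Ophthalmoscopy records whether cataract is present (Protocol 4.3.3.4).
- Safety analysis is descriptive, and both the placebo arm and the improved column give a reference for noise. At s = 0.05 the Step 3 model leaves about 68% of unchanged eyes in the no-change class; at s = 0.10 it leaves about 38%.

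All of this stands. A reader might infer that the plan cannot detect serious visual loss, but the documents do not support that. The limitation belongs to the three-class table.

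Two other inferences also fail:

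- **Conflict over population.** It is tempting to read 3.5.7 as putting visual safety data in the ITT population, against the as-treated population in 3.9. The ITT sentence covers only the physical and neurological examinations; none is named for the visual summaries. ITT here also requires a dose, so the practical difference is grouping by randomized or by actual treatment.
- **Misleading mean change.** The section plans summary statistics of acuity values and categories of change. It does not specify a mean change.

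Finally, the later SAP no longer produces the table. With 29 subjects, a fall from 1.0 to 0.1 can be seen directly in a listing.

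**Conclusion.** The point holds for original SAP 3.5.7 and is minor. The only change-from-baseline table planned for acuity has no size band, and decimal differences do not rank losses correctly. Both follow from the stated rule and simple arithmetic.

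The amount of noise is less certain. The 16% to 31% range depends on one-line steps and a retest SD of 0.05 to 0.10 logMAR, neither of which the documents give. It applies to one eye at one visit. The 18.2 against 15.2 comparison also assumes a 5% rate of severe loss and shows dilution only, because no test of safety data is planned.

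The defect has no effect on the outputs planned in the later SAP. The absence there of a flag for large losses is a matter of convenience.

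**What to change.** In original SAP 3.5.7:

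1. Derive logMAR for each eye as −log10 of the decimal value already collected. State a rule for an entry of 0, where the logarithm is undefined.
2. Replace the three classes with graded bands of loss per eye, for example at least 0.2 and at least 0.3 logMAR. These cut-offs are illustrative, and the sponsor should justify its own. Under the Step 3 assumptions a 0.2 band still catches Φ(−0.15/s) of unchanged eyes, from 0.1% (s = 0.05) to 6.7% (s = 0.10).
3. Report the bands at the worst post-baseline value and at the last visit. The worst value has several chances to cross a band by noise, so it should be read against placebo.
4. Name the population: actual treatment in the as-treated population, in line with original SAP 3.9.

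The cost is one derived variable and one revised table, with no new data. In the later SAP, a listing flag on large losses is optional.

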### **3.5.8 Protocol Deviations**

Protocol deviations (PDs), will be recorded and are classified as major and minor deviation under following categories:

- Did not fulfil eligibility criteria
- Developed discontinuation criteria but continued IP treatment
- Received incorrect investigational treatment/dose
- Received prohibited concomitant medication
- Protocol-required procedure not adhered to
- Other

Tabulation of major protocol deviations by category will be provided by treatment group. The number of percentage of subjects who had at least one major protocol violation or deviation will be summarized in total and by treatment group. A supporting data listing will be provided as well.

### **3.6 Efficacy Analyses**

Efficacy data from the DB treatment period and the OL treatment period will be analyzed separately. All efficacy endpoints will be summarized by treatment group.

